Parameter	Higher Limit
QRS interval	QRS ≥ 115 msec
PR interval	PR > 225 msec
QTc	> 480 msec

ECG = electrocardiogram; QTc = QT interval corrected for heart rate

Subjects **may** also be prematurely discontinued from the study for reasons of safety including those who experience:

- A vital sign, ECG, and/or laboratory abnormality judged to be clinically significant by the investigator and that in the opinion of the investigator or the sponsor is possibly related or related to the study intervention
- An intolerable AE (defined as an AE that subjectively would cause a subject to consider study withdrawal), as determined by the investigator or the Sponsor.

Additionally, discontinuation of study intervention for abnormal liver function should be considered by the investigator when a subject meets the criteria for Hy's law or the appearance of abnormal laboratory test results suggesting severe drug-induced liver injury (DILI), or if the investigator believes that it is in best interest of the subject. If Hy's law criteria are met and it is considered, in the opinion of the investigator or the Sponsor, to be possibly related to the study drug, the subject must be discontinued from the study. Refer to [Appendix E](#) for additional information.

All enrolled subjects who prematurely discontinue from the study, regardless of cause, should be seen for the assessments to be completed at the End of Treatment (EOT) Visit. The EOT assessments are defined as completion of evaluations scheduled for all subjects.

Subjects who discontinue from the study and do not return to the study site for EOT Visit (Visit 5) must be requested in writing to return to the study site for procedures required at the EOT Visit as defined in the Activity Schedule ([Appendix D](#)) and return any unused study intervention. A copy of the letter, together with the source documentation, will be kept in the investigator's files. The reason for premature discontinuation from the study will be recorded on the Study Termination Page of the electronic case report form (eCRF). Study site staff will be contacted by the sponsor after each premature discontinuation to ensure proper characterization of the reason for discontinuation is captured.

See the Activity Schedule ([Appendix D](#)) for data to be collected at the time of study intervention discontinuation and follow-up and for any further evaluations that need to be completed.

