5.6 Follow-Up After Subject Discontinuation of Study Drug or from Study

To minimize missing data for efficacy and safety assessments, subjects who prematurely discontinue study drug treatment due to an AE should continue to be followed for all regularly scheduled visits, unless subject's LAR/parent/guardian has decided to discontinue the study participation entirely (withdrawal of informed consent). Subjects should be advised on the continued scientific importance of their data even if they discontinue treatment with study drug early.

If a subject prematurely discontinues study participation (withdrawal of informed consent), the procedures outlined for the Premature Discontinuation visit (PD visit) should be completed as soon as possible, preferably within 2 weeks of the last visit. In addition, if the LAR/parent/guardian is willing, the 1-week postintervention visit (after the last dose of study drug) may be completed to ensure all treatment-emergent AEs/SAEs have been resolved.

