5.7 Study Drug

Study drug will be administered at the study site after confirming eligibility.

Study drug dose preparation and administration instructions will be provided separately.

Linaclootide (or matching placebo for Part 2 only) will be taken orally once daily beginning on Day 1 (Baseline) and should be taken at approximately the same time each day, 15 - 30 minutes before a meal. If subjects should forget to take their study drug dose at their regularly scheduled dosing time, they

should take the forgotten dose as soon as they remember as long as it is at least 15 - 30 minutes before their next meal. Otherwise, they should take the next dose at the next scheduled dosing time; subjects may eat 15 - 30 minutes after dosing. No redosing will be allowed on the same day.

The subject must complete at least 4 weeks (28 days) intervention period before returning for the Week 4/Day 29 End of Treatment (EOT) (Visit 5).

Subject dosing will be recorded on a subject dosing eDiary. The LAR/parent/guardian will be instructed to return all drug containers (even if empty) to the study site personnel at each study visit. If required, the LAR/parent/guardian should also return the receptacle containing unused solution to the study site personnel for destruction. The study site personnel will document compliance.

AbbVie will provide study drug for linaclotide (or matching placebo for Part 2 only). AbbVie provided study drug should not be substituted or alternately sourced unless otherwise directed by AbbVie. Study drug will only be used for the conduct of this study.

If a subject's LAR/parent/guardian is unable to come to the study site to pick up the subject's study drug due to COVID-19, a direct-to-patient (DTP) study drug shipment can be made from the study site to the subject's LAR/parent/guardian if allowed by local regulations. AbbVie will submit any required notifications to the regulatory authority as applicable. Refer to the Operations Manual in [Appendix G](#) for details on DTP shipment of study drug.

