- b. Study site staff will verify compliance with the eDiary and remind LAR/parent/guardian/caregivers to complete their assessments daily. Assessment of global change in symptoms and global severity of symptoms will be completed in the weekly Diary. The global severity items will be completed beginning at the Preintervention Period through the 1-week postintervention visit (Visit 6), and the global change items will be completed from one week after enrollment/randomization through the 1-week postintervention visit (Visit 6).
- c. Vital signs include weight, temperature, and respiratory rate. Postural vital signs (supine and standing whenever possible according to subject's age) include pulse rate and systolic and diastolic blood pressure. Blood pressure and pulse measurements should be preceded by at least 5 minutes of rest for the subject in a quiet setting. At all visits, postural vital signs must be obtained after subjects have been in a supine position for at least 2 to 3 minutes, followed by a standing position for at least 1 minute. If possible, temperature should be obtained using the same method at each visit.
- d. The optional PK sample can be collected either before or after subjects receive study drug. Optional PK samples should be collected at the same time as clinical labs. This visit should be scheduled at approximately the same time as when subjects take their daily dose. Refer to Section 3.8 for additional details.
- e. The subject must complete at least 4 weeks (28 days) of intervention period before returning for the Week 4/Day 29 EOT or premature discontinuation visit (Visit 5). The study drug will be administered at approximately the same time as on other days of study drug administration.
- f. Protocol-permitted rescue medication (outlined in Section 5.3 of the protocol) will be site-supplied or site-dispensed from preintervention to Week 4 (Visits 2-5). The LAR/parent/guardian may choose a different protocol-permitted rescue medication at any subsequent visit, where available. Additional protocol permitted rescue medications may be site-supplied or site-dispensed as needed at any subsequent visits, where available.
- g. Rescue medication will be recorded, refer to Section 3.3 for details.

WEEK 4 (Visit 5 Day 29 EOT or premature
discontinuation [+ 2 Days]):

INTERVIEW	
 • Rome IV Assessment • Assess Rome IV status^a • Adverse event assessment • Prior/concomitant therapy

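### The Operations Manual sets a 28-day minimum before the premature discontinuation visit; read literally, this conflicts with Protocol 5.6 and 5.7 and can delay the only scheduled post-baseline safety tests in children who leave the study early

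*Protocol*

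**What the plan says.** **The 28-day condition.** Operations Manual 2.1, Week 2 (Visit 4), footnote e says that a child "must complete at least 4 weeks (28 days) of intervention period before returning for the Week 4/Day 29 EOT or premature discontinuation visit". The heading of the next visit begins "Visit 5 Day 29 EOT or premature" and carries a plus-only window of 2 days. Appendix D of the protocol likewise puts EOT and premature discontinuation in one column. Protocol 5.7 has nearly the same sentence as footnote e, but for EOT alone: a child "must complete at least 4 weeks (28 days) intervention period before returning for the Week 4/Day 29 End of Treatment (EOT) (Visit 5".

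**Leaving the study.** Protocol 5.6 reads "If a subject prematurely discontinues study participation (withdrawal of informed consent), the procedures outlined for the Premature Discontinuation visit" and goes on to say that these procedures "should be completed as soon as possible, preferably within 2 weeks of the last visit".

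**Stopping drug but staying in.** Protocol 5.6 also says that "subjects who prematurely discontinue study drug treatment due to an AE should continue to be followed for all regularly scheduled visits".

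**Any premature discontinuation from the study.** Protocol 5.5 says that such subjects "should be seen for the assessments to be completed at the End of Treatment (EOT) Visit". It gives no date, and neither does Visit 5 footnote h in the Operations Manual. The same section lists events for which a child must be taken out of the study, among them an AESI and a possibly related SAE.

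**The tests at stake.** By Appendix D and the visit lists in Operations Manual 2.1, chemistry, hematology and ECG are scheduled at Screening and Visit 5 only. Visit 4 has an optional PK sample, and Visit 6 has vital signs but no laboratory test or ECG.

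**The concern.** A child who discontinues early has, by definition, not had 28 days of intervention. If the intervention period in footnote e means days on drug, the condition can never be met. If it means calendar time, the child waits until Day 29. Neither fits Protocol 5.6 for a child who leaves the study.

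Investigators agree in Appendix B to follow both the protocol and the Operations Manual, so a site holds two instructions that disagree. The gap is widest for a child removed for safety under 5.5. The timing in 5.6 is tied to withdrawal of consent and 5.5 has none, so the only calendar day attached to that child's visit is the manual's Day 29.

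Two of the three AESI categories in Protocol 6.1 are electrolyte and ECG abnormalities due to diarrhea. The absence of treatment-related AESIs is one of the two dose-selection criteria in Protocol 4.1. If the only scheduled post-baseline sample is taken well after the last dose, it says little about the child on drug. Apart from the 30-day limit for potential Hy's Law, the SAP does not classify laboratory or ECG values by time since last dose. SAP 10.5 refers to an intervention period for ECG values, but does not say when that period ends for an early stopper.

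**Working it through.** This is day arithmetic. No sample-size or power figure enters.

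**Inputs.** First dose and Visit 3 on Day 1; Visit 4 on Day 15 (window Day 13 to 17); Visit 5 on Day 29 (window to Day 31), all from Appendix D and Operations Manual 2.1. The outer preferred limit of 2 weeks after the last visit is from Protocol 5.6. Last-dose days are assumed and shown as a range. The last visit is taken as the last one attended.

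**The plan's own figure.** 28 dosing days from Day 1 end on Day 28, so the visit falls on Day 1 + 28 = Day 29. This reproduces.

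**Formulas.**
- Lag under the literal footnote = 29 minus last-dose day, up to 31 minus last-dose day.
- Outer preferred day under 5.6 = day of last visit + 14.
- Excess = Day 29 to 31 minus that outer preferred day.

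| Last dose (assumed) | Last visit | 5.6 outer preferred day | Lag at that day | Lag at Day 29 to 31 | Excess, days |
|---|---|---|---|---|---|
| Day 1 | Day 1 | Day 15 | 14 | 28 to 30 | 14 to 16 |
| Day 3 | Day 1 | Day 15 | 12 | 26 to 28 | 14 to 16 |
| Day 7 | Day 1 | Day 15 | 8 | 22 to 24 | 14 to 16 |
| Day 10 | Day 1 | Day 15 | 5 | 19 to 21 | 14 to 16 |
| Day 14 | Day 1 | Day 15 | 1 | 15 to 17 | 14 to 16 |
| Day 15 | Day 15 | Day 29 | 14 | 14 to 16 | 0 to 2 |
| Day 22 | Day 15 | Day 29 | 7 | 7 to 9 | 0 to 2 |
| Day 25 | Day 15 | Day 29 | 4 | 4 to 6 | 0 to 2 |

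If Visit 4 took place on Day 13, the outer preferred day is 27 and the excess is 2 to 4 days. If on Day 17, it is Day 31 and the excess is -2 to 0 days.

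**By type of discontinuation.**
- Leaves the study before Visit 4: the two texts differ by 14 to 16 days at the outer limit, and by more if the visit is held promptly.
- Leaves after Visit 4: the outer dates nearly coincide. What still differs is that 5.6 asks for the earliest possible visit.
- Stops drug for an adverse event and stays in: Day 29 under both texts.
- Removed for safety under 5.5: no interval in the protocol; Day 29 is the only day given.

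One child in a six-child cohort is 1/6 = 17% of the laboratory and ECG denominator.

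**The case against.** The strongest reply is that this is a drafting slip. Visit 5 is named for both purposes, and footnote e looks like the sentence in 5.7 with the full visit name pasted in. A condition that cannot be met is unlikely to be applied as a waiting rule, footnote h sets no wait, and the heading can be read with Day 29 belonging to EOT alone. That may well be the origin. It does not remove the conflict, because the text as issued is what sites are told to follow.

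Three stronger readings are tempting, and the documents do not support them.

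- *That the footnote delays testing in every child who stops drug for diarrhea.* Protocol 5.6 keeps children who stop for an adverse event but remain in the study on the regular visits. Their Visit 5 would be at Day 29 without the footnote.
- *That a child goes unassessed until Day 29.* Caregivers are told to stop the drug and contact the investigator at onset of an AESI. Adverse events are followed to a conclusion, symptom-directed examinations are allowed at any time, and Operations Manual 3.15 permits unscheduled safety samples. These samples are permitted, not required, so they lessen the gap without closing it.
- *That recovered values bias the safety tables towards normal throughout.* SAP 10.3 includes local and SAE-related laboratory data, tabulates shifts to the minimum and maximum, and counts any post-baseline PCI value. An abnormal value once sampled is kept. What remains exposed is the final-value shift table, and any child whose late sample is the only one.

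Frequency also matters. The protocol reports no adverse-event discontinuations among 35 children aged 2 to 5 years in LIN-MD-67, and 1.2% on linaclotide in LIN-MD-64. Those children were older, so the figures are only indicative, but few such cases should be expected.

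**Conclusion.** The concern holds in limited form. Footnote e, together with the Visit 5 heading, conflicts as written with Protocol 5.7 and, for children who leave the study, with Protocol 5.6. Protocol 5.5 and footnote h do not resolve it, because they require the assessments without dating them.

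The consequence is material for a child who leaves before Visit 4: the only scheduled post-baseline chemistry, hematology and ECG can fall about 2 to 4 weeks after the last dose. After Visit 4 there is little numeric conflict, and a last dose after Day 22 can give a lag of less than a week.

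This rests on reading the intervention period as calendar time and on assumed last-dose days. No discontinuation rate in this age group is available. It is worth correcting because it is an operational instruction that touches safety data in very small cohorts.

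**What to change.** In the Operations Manual, remove the reference to the premature discontinuation visit from the 28-day condition in footnote e, and separate that visit from the Day 29 date in the Visit 5 heading. Reconcile both with Protocol 5.5, 5.6 and 5.7, so that the timing is stated for each type of discontinuation: withdrawal of consent, removal for safety under 5.5, and stopping drug while remaining in the study. The interval is for the sponsor to decide. This does not call for a new visit rule for every child who stops drug, which would cut across the regular schedule in 5.6 and could bring forward the end-of-treatment Rome IV assessment.

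In the SAP, add a variable for days since last dose to post-baseline laboratory and ECG values. Use it to mark late off-drug values, above all in the final-value shift table and where no other post-baseline sample exists, so that they are not read as on-treatment results.

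The cost is wording changes and one derived variable. No procedure is added.

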2.2 Individual Post-Treatment Period Visit Activities

This section presents a list of activities performed during each visit, organized by visit. The dot pattern on the upper right indicates the place of the visit in the overall Post-Treatment Period Activity Schedule.

Activities are grouped by category (Interview, Exam, etc.). Further information about the activities is presented in Section 3.

1-week postintervention Visit [(Visit 6, Day 29) 7

days + 2 Days]:

 INTERVIEW	
• Adverse event assessment• Prior/concomitant therapy
 Observer Reported Outcome	
• eDiary Compliance^a• Return eDiary device^b
 EXAMS	
• Vital signs (including weight) and Postural Vital Signs^c

NOTE: All procedures must be performed onsite. All assessments must be recorded in the source records in addition to the eCRF. Rescue medication will be recorded, refer to Section 3.3 for further information.

- a. At the Preintervention Visit, LAR/parent/guardian/caregivers will be trained on the use of the eDiary device and instructed to complete the daily evening assessment. At subsequent visits, study site staff will verify compliance with the eDiary and remind LAR/parent/guardian/caregivers to complete their assessments daily. The global severity items will be completed beginning at the Preintervention Period through the 1-week postintervention visit (Visit 6), and the global change items will be completed from one week after enrollment/randomization through the 1-week postintervention visit (Visit 6).
- b. The subject's LAR/parent/guardian/caregiver will return the eDiary device.
- c. Vital signs include weight, temperature, and respiratory rate. Postural vital signs (supine and standing whenever possible according to subject's age) include pulse rate and systolic and diastolic blood pressure. Blood pressure and pulse measurements should be preceded by at least 5 minutes of rest for the subject in a quiet setting. At all visits, postural vital signs must be obtained after subjects have been in a supine position for at least 2 to 3 minutes, followed by a standing position for at least 1 minute. If possible, temperature should be obtained using the same method at each visit.

3 STUDY PROCEDURES

3.1 Study Subject Information and Informed Consent

The investigator or their representative will explain the nature of the study, including the use and assessment of any investigational devices (e.g., the eDiary) to the LAR/parent/guardian/caregiver of the subject, the benefits and risks anticipated from participation in the study, and answer all questions regarding this study. Prior to any study-related screening procedures being performed on the subject or any medications being discontinued by the subject in order to participate in this study, the informed consent statement will be reviewed, signed, and dated by the subject's legally authorized representative (LAR)/Parent/guardian, the person who administered the informed consent, and any other signatories according to local requirements. A copy of the signed informed consent will be given to the subject's LAR/parent/guardian and the original will be placed in the subject's medical record. An entry must also be made in the subject's dated source documents to confirm that informed consent was obtained prior to any study-related procedures and that the subject received a signed copy.

Information regarding benefits for subjects and information regarding provisions for treating and/or compensating subjects who are harmed because of participation in the study can be found in the informed consent form.

Samples for optional pharmacogenetic analyses or other exploratory analyses will only be collected if the LAR/parent/guardian of the subject has voluntarily signed and dated a separate written consent form for this testing that has been approved by an IRB/IEC, after the nature of the testing has been explained and the subject has had an opportunity to ask questions. The separate written consent may be part of the main consent form. If the subject does not consent to the testing, it will not impact the subject's participation in the study.

3.2 Medical History

A complete medical history including demographics will be taken at screening. The subject's medical history will be updated at the Study Day 1 visit. This updated medical history will serve as the baseline for clinical assessment.

3.3 Rescue Medications

Refer to Table 2 of Protocol Section 5.3 for the protocol-permitted rescue medications. Of note,

- Any laxatives are to be discontinued prior to the Preintervention Visit in favor of the site-supplied, protocol-permitted rescue medications.
- Rescue medication is not to be used on the calendar day before enrollment/randomization (Visit 3) and on the day of the enrollment/randomization Visit (Visit 3) until randomization/enrollment.
- Rescue medication (name of medication, dose, and route of administration) records will include medication given by the caregiver/parent/guardian/LAR as well as information from secondary caregivers if the participant was in the care of others. Rescue medication is recorded in the EDC and the eDiary.
- Rescue medication may be taken when at least 72 hours have passed since the subject's previous BM or when their symptoms become intolerable.

3.4 Lifestyle Modifications

During the Preintervention Period, LAR/parent/guardians will be advised to have subjects adopt the following nonpharmacologic habits and instructed to maintain them throughout the study.

- Adequate fluids: The investigator will discuss the fluid intake necessary to maintain a hydrated state (intake requirements may vary amongst children e.g., child athletes, children in hot climates).
- A high-fiber diet: High-fiber foods include beans, whole grains, fruits, and vegetables. Start slowly, adding just several grams of fiber a day over the Screening Period to reduce the amount

of gas and bloating that can occur in someone who is not used to consuming high-fiber foods. The optimum intake of dietary fiber for infants and children younger than two years of age is not known. Studies of weaning diets with the gradual introduction of solid foods, including increased fiber, suggest that an intake of 5 g per day is beneficial provided the children ingest adequate calories, vitamins, and minerals. ^{1,2}

- Increased physical activity: Subjects should be physically active throughout the day. Caregivers of subjects should encourage active play that includes a variety of activity types.
- Adequate time for bowel movements:
 - LAR/parents/guardians will be requested not to start the toilet training process with their child during the child's participation in the study. Changes in toileting skills may impact bowel habits and accurate reporting of bowel movements and fecal incontinence.

3.5 Rome IV Assessment

As outlined in Section 5.1 of the protocol, the subject meets the Rome IV criteria for FC.

For at least 1 month before Screening (Visit 1), the subject must meet 2 or more of the following symptoms:

- history of excessive stool retention;
- history of painful or hard bowel movements (BMs);
- presence of a large fecal mass in the rectum;
- history of large-diameter stools;
- 2 or fewer defecations per week [with each defecation occurring in the absence of any laxative, suppository, or enema use during the preceding 24 hours].

Accompanying symptoms may include irritability, decreased appetite, and/or early satiety. The accompanying symptoms disappear immediately following passage of a large stool.

